### **8.2. Populations for Analysis**

All subject protocol deviations will be summarized in the clinical study report. All exclusions from the per-protocol population will be reviewed in a blind data review meeting before breaking the blind.

#### **8.2.1. Modified intention-to-treat analysis (MITT)**

The modified intention-to-treat (MITT) population will include all randomized subjects who were dispensed study medication and provided any post-baseline efficacy data.

The MITT analysis provides estimates of treatment effects that may be more likely to mirror those effects observed in subsequent practice. Consequently, this analysis will be considered the primary efficacy analysis.

#### **8.2.2. Safety Population**

The safety population will include all randomized subjects who received at least 1 dose of study drug. The analysis of safety will include variables such as clinical laboratory evaluations, vital signs, and adverse drug experiences. It is not necessary that measurements of any efficacy variable post randomization be available.

#### **8.2.3. Per-protocol analysis (PP)**

The per-protocol (PP) population is a subset of the MITT population and includes subjects who have no violations of the inclusion/exclusion criterion and who are compliant with treatment medication, defined as greater than or equal to 80% of specified medication. Before breaking the blind the precise reasons for excluding subjects from the PP population will be fully documented in a blinded data review meeting.

### **8.3. Interim Analysis**

No interim analyses are planned.

### **8.4. Subgroup Analysis**

Subgroup analyses including but not limited to race, age and sex will be performed for exploratory purposes on all secondary efficacy variables for the MITT population, provided adequate sample sizes are available in potential subgroups. Subgroup analyses performed on the PP population are considered exploratory.

### **8.5. Baseline Characteristics**

#### **8.5.1. Definition of Baseline**

Baseline will be the data collected at Visit 2.

#### **8.5.2. Demographic and Baseline Data**

Demographic data will be collected at the screening visit. The demographic data to be collected will include date of birth (age), sex at birth, race and ethnicity.

Accutis, Inc.

Protocol number: ACU-D1-201

Subject demographic and baseline characteristics will be summarized for the MITT and PP set of subjects. Continuous variables will be summarized using descriptive statistics (n, mean, standard deviation, median, minimum and maximum), and categorical variables will be summarized using the count and percentage of subjects in each category.

Demographics will be provided in a subject listing.

### **8.5.3. Medical History**

The medical history data will be collected at the Visits 1 and 2.

Verbatim terms for Medical History will be mapped to their corresponding thesaurus terms (preferred term and system organ class) from the Medical Dictionary for Regulatory Activities (MedDRA) coding dictionary, version 21.0. Summaries will be made using the assigned preferred terms, and will be based on the number and percentage of subjects having at least one occurrence

Analysis will include frequencies and proportions of patients reporting Medical History findings using the preferred terms and system organ class.

All conditions will be provided in a subject listing.

### **8.5.4. Medications**

Medication will be mapped to their corresponding ATC code from the WHO Drug Dictionary, version 2018. Summaries will be made using the Level 3 and 4 codes terms, and will be based on the number and percentage of subjects having at least one occurrence for all subjects in the Safety population.

Concomitant medications will be presented in a listing.

## **8.6. Subject Disposition**

Subject disposition summary will include the number and percentage of subjects in each of the following categories:

- Subjects completing the study
- Subjects withdrawn early from study
- Reasons for discontinuation from study

Percentages will be based on the number of subjects randomized.

Subject disposition will be presented in a listing.

## **8.7. Study Visits**

The number and percentage of subjects at each scheduled visit will be tabulated. By-subject data listing for visit participation will be prepared.

## **8.8. Protocol Deviations**

The number and percentage of subjects who do not meet all of the inclusion and exclusion criteria will be tabulated by treatment group. The number and percentage of subjects who had a significant protocol deviation will be also tabulated.

By-subject listings of screen failures and protocol deviations will be prepared.

### **8.9. Extent of Exposure**

Extent of exposure will be defined as the total ordinal number of days a subject is exposed to any study treatment. This will be calculated for each subject by taking the difference between the visit at which the first administration of study treatment took place and the date of last application. For subjects who are lost to follow-up, extent of exposure will be calculated based on the last study visit attended.

A summary of the number of days of exposure will be prepared for subjects in the Safety population.

The data for extent of exposure will be presented in a listing.

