5.4.2. Visit 2 (Day 1); randomization and start of treatment period

This visit should occur within 14 days after Visit 1. Subsequent study visit dates must be scheduled based on the date of this visit.

Prior to this visit the investigator/designee must confirm that all items necessary to determine the subject's eligibility for randomization are available.

At this visit, the investigator or designee will perform the following procedures PRIOR TO RANDOMIZATION:

1. Query the subject in a non-directive manner about any changes in her/his health since the previous visit and report any changes that are, in the investigator's opinion, meaningful, as Medical History
2. Query the subject about any changes in her/his concomitant therapies since the previous visit and report changes on the appropriate form
3. Confirm the subject continues to comply with all study restrictions and has followed all study instructions
4. Measure vital signs
5. Perform a Lesion Count; a total of ≥ 10 and ≤ 40 inflammatory lesions (papules, pustules and nodules) and ≤ 2 nodules on the treatment area is required
6. Perform an IGA; a score of ≥ 3 (moderate to severe) is required
7. Determine the subject's eligibility for randomization
8. Discharge from the study subjects who are not eligible for randomization.

For subjects who are eligible for randomization the investigator or designee will perform the following procedures:

1. Take standardized color photographs
2. Have the subject perform a pre-treatment Local Tolerability Assessment (LTA)
3. Perform a pre-treatment LTA
4. Randomize eligible subjects
5. Dispense study medication to the subject
6. Instruct the subject on the proper study medication application technique
7. Observe the subject's first study medication application
8. Monitor the subject for at least 20 minutes after the Application Completion Time to detect any adverse events
9. Have the subject perform a post-treatment LTA 10 (± 4) minutes after the Application Completion Time
10. Perform a post-treatment LTA 20 (± 4) minutes after the Application Completion Time
11. Review the study instructions with the subject
12. Schedule Visit 3.

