5.6. Study Medications

5.6.1. Study medication identity

The study medications are white to off-white colored ointments and are indistinguishable in physical appearance. The study medications must be maintained at the investigational center in a secure area with limited access under appropriately controlled and monitored storage conditions. Study medications must be stored in a refrigerator at the investigational center.

Study Medication Information		
Study medication name	ACU-D1 Ointment [REDACTED]	ACU-D1 Ointment Vehicle
Manufacturer	[REDACTED]	
Active ingredient	PTTC	None
Active concentration	[REDACTED]	0%
Pharmaceutical Form	Ointment	
Storage Conditions	[REDACTED]	
Dose regimen		
Route	Topical	
Frequency	Twice daily	
Duration of administration	84 days (12 weeks)	

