## **6. TRIAL DESIGN**

This is a randomized, double-blind, vehicle-controlled, parallel-group study of ACU-D1 Ointment [REDACTED] and the ACU-D1 Ointment Vehicle in subjects with papulopustular rosacea on the face.

Subjects will be randomized in a 2:1 ratio with 24 subjects randomized to treatment with ACU-D1 Ointment [REDACTED] and 12 subjects randomized to treatment with ACU-D1 Ointment Vehicle

The study will be conducted at two United States investigational centers.

Study visits are:

- Visit 1 (Day -13 to 0) enrollment and start of the screening period
- Visit 2 (Day 1) randomization and start of the study medication treatment period

Accutis, Inc.

Protocol number: ACU-D1-201

- Visit 3 (Day 15) treatment period follow-up
- Visit 4 (Day 29) treatment period follow-up
- Visit 5 (Day 57) treatment period follow-up
- Visit 6 (Day 85) end of the treatment period and start of the no treatment follow-up period
- Visit 7 (Day 99) no treatment follow-up, end of study.

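### SAP 8.9 defines extent of exposure as a count of days but computes a plain date difference, which omits a treated day and gives a Day-1-only user zero days

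*SAP*

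**What the plan says.** SAP 8.9 first says what the quantity is: "the total ordinal number of days a subject is exposed to any study treatment". It then says how to obtain it: "the difference between the visit at which the first administration of study treatment took place and the date of last application". No added day and no inclusive-count rule is stated there or elsewhere in either document. A further sentence sets a different end point for some subjects: "For subjects who are lost to follow-up, extent of exposure will be calculated based on the last study visit attended". The result is summarised for the safety population and listed by subject.

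The starting point is fixed by the visit schedule. SAP 6 has "Visit 2 (Day 1) randomization and start of the study medication treatment period", and Protocol 5.4.2 requires site staff, at that visit, to "Observe the subject's first study medication application". The scheduled end is "Visit 6 (Day 85) end of the treatment period and start of the no treatment follow-up period". Protocol 5.6.1 gives the planned duration of administration as 84 days, and SAP 8.2.2 admits to the safety population any randomized subject who received at least one dose.

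**The concern.** The definition and the calculation sit in one paragraph and give different answers. A difference between two dates counts the intervals between them, which is one fewer than the number of calendar days from the first to the last inclusive. Day 1 is certainly a treated day, because the application is observed at the site, yet the subtraction drops it.

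The error is most visible in a subject who applies once at Visit 2 and then stops, for example because of intolerance. That subject counts as treated for every safety table but would show no exposure. Safety and tolerability are part of the main objective and only about 36 subjects are planned, so a single such row would be noticed in the listing and would set the reported minimum.

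**Working it through.** **Inputs.** First application on Day 1 (SAP 6; Protocol 5.4.2). Visit 6 on Day 85, that is 84 ± 4 days after Visit 2 (Protocol 5.4.6). Planned duration 84 days (Protocol 5.6.1). No application within 6 hours before a visit (Protocol 5.6.6). The SAP gives no worked exposure figure.

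**The planned 84 days.** The figure can be reproduced in two ways: as an inclusive count of Days 1 to 84 (84 − 1 + 1 = 84), or as elapsed days from Visit 2 to Visit 6 (85 − 1 = 84).

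**Known last application date, no missed days.** Let L be the study day of last application. The SAP rule gives L − 1, and the days actually exposed are L − 1 + 1 = L. The relative shortfall is 1/L.

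| L | SAP rule | Days exposed | Shortfall |
|---|---|---|---|
| 1 | 0 | 1 | 100% |
| 15 | 14 | 15 | 6.7% |
| 29 | 28 | 29 | 3.4% |
| 57 | 56 | 57 | 1.8% |
| 84 | 83 | 84 | 1.2% |
| 85 | 84 | 85 | 1.2% |

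**Missed whole days.** Let g be the number of whole days without any application, with the last application on Day 84. The rule still gives 83, while the days exposed are 84 − g, so the error is 83 − (84 − g) = g − 1. For an assumed g of 0, 1, 2, 3 and 4 the error is −1, 0, +1, +2 and +3. The shortfall vanishes at one missed day and becomes an overcount from two. Protocol 5.6.8 requires removal only after more than 4 consecutive days without full application, so gaps can occur in subjects who stay in the study.

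**Lost to follow-up.** Let V be the study day of the last visit attended and a the true day of last application, with no gaps. The rule gives V − 1 and the truth is a, so the error is V − 1 − a. Assume that a lies between 1 day before and 13 days after V. For V = 15, 29 or 57 the error then runs from V − 1 − (V − 1) = 0 to V − 1 − (V + 13) = −14. If Visit 2 was the last visit attended, the rule gives 1 − 1 = 0 whatever was applied afterwards.

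**Where the variable is used.** Compliance comes from diary counts of applications (SAP 8.10). Per-protocol membership rests on eligibility and the 80% medication criterion (SAP 8.2.3), and safety membership on having received a dose (SAP 8.2.2). Adverse events are summarised as numbers and percentages of subjects (SAP 8.12.1). The efficacy models in SAP 8.11 contain no exposure term.

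**The case against.** The strongest defence is that the paragraph is loosely worded rather than wrong. The definition speaks of an ordinal number of days, and the study numbers its days with Visit 2 as Day 1, so a programmer working from the definition would count Day 1 as one. This confirms that an inclusive count was intended, but the sentence that tells the programmer what to compute does not deliver it.

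Three stronger readings are tempting, and the documents do not support them.

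- A reader might infer that every subject is one day short. The exact one-day shortfall needs a known last application date and no missed days. Subjects lost to follow-up have their own rule in the same section, and missed days can cancel or reverse the shortfall.
- A reader might infer that anyone who completes the course is shown below plan. That holds if the last application falls on Day 84. The 6-hour restriction permits an application early on Day 85 before a later visit, and the SAP rule then gives 84, equal to the planned figure. The corrected count is 85. With a window of ± 4 days around Visit 6, one day either way says little about completion.
- A reader might infer that rates or compliance figures with exposure as denominator are inflated, or undefined at zero. No such figure is planned. Nor is a Day-1-only subject removed from any population.

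It is also fair to say that adding 1 does not by itself make the figure a count of days exposed, because a first-to-last span still ignores gaps.

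**Conclusion.** The point stands as a minor inconsistency in a reported safety figure. The stated calculation does not return the stated quantity. The shortfall is exactly one day for subjects with a known last application date and no missed days, which is negligible for a full course and total for a Day-1-only user. Among those subjects the shift is the same in both arms, so it does not distort the comparison between them.

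The sizes given for missed days and loss to follow-up rest on assumed ranges (0 to 4 missed days; last application from 1 day before to 13 days after the last visit attended), because the documents give no figures for either. Nothing beyond the exposure summary and listing changes.

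**What to change.** In SAP 8.9:

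1. State extent of exposure = date of last application − date of first application + 1.
2. Apply the same term for subjects lost to follow-up: date of last visit attended − date of first application + 1. This makes the two rules consistent and prevents a zero. It does not recover the unknown stop date: under the range assumed above, the error becomes +1 to −13 days (0 + 1 and −14 + 1), so the listing should mark these values as imputed.
3. State that the figure is a first-to-last span from which missed days are not subtracted, or else subtract them.

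The cost is a sentence or two in the SAP and one term in the program, with a little more programming if missed days are subtracted. The changes to the day count add no data collection and leave all other analyses as they are.

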### **8.10. Compliance**

Compliance will be assessed from subject daily diaries in which the number of applications will be captured. The overall percent compliant (<80% and ≥80%) will be tabulated for the MITT and PP populations and also compliance by visit will be summarized.

Compliance information will also be presented in a by-subject listing.

### **8.11. Efficacy Analyses**

#### **8.11.1. Primary Efficacy Variables: Lesion Count**

Total lesion count will be summarized for each treatment group and at each visit using mean, standard deviation, median, minimum, and maximum. The comparison between the two treatments will be based on the difference for each subject between each visit and Visit 2.

In accordance with ICH E9 guideline on Statistical Consideration in the Design of Clinical Trials (1998), the type 1 error rate of the test will be 5%.

Proc Mixed in SAS will be used to develop a repeated measures analysis of covariance (ANCOVA) model to test the null hypothesis of no treatment effect. The dependent variable will be the difference between the value at each post-baseline visit, including endpoint, and the baseline value. The change from baseline to the endpoint (Visit 6) will be the primary efficacy endpoint. The baseline value will be the covariate. Treatment group and study center will be the main effects in the model. The mixed model will employ LOCF procedures for missing values. Efficacy will be declared if the treatment effect p-value for the MITT population is no greater than 0.05 and is favorable to ACU-DI Ointment [REDACTED]

A second ANCOVA, which includes a treatment-by-center interaction, will be performed in order to test the significance of the interaction term in an exploratory manner. If the interaction term is significant at the 0.10 level, summary data will be presented for each study center in an appendix to the study report. In addition, if the interaction term is significant at the 0.10 level, the interaction term may be included in the final ANCOVA model to examine treatment effects if inclusion of this term increases the sensitivity of the analysis.

The residuals from the primary ANCOVA model will be analyzed for deviations from normality. If the test for normality fails at the 0.05 level of significance then the ANCOVA analysis will be supplemented by a Van Elteren test using Proc Npar1way in SAS, stratified by study center. Subgroup analyses including but not limited to race, age and gender will be performed for exploratory purposes, provided adequate sample sizes are available in potential subgroups. Subgroups will be analyzed by adding the subgroup as a main effect and the interaction term of subgroup\*treatment to the model.

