9.3.2. Statistical analysis of total lesion count

Total lesion count will be summarized for each treatment group and at each visit using mean, standard deviation, median, minimum, and maximum. The comparison between the two treatments will be based on the difference for each subject between each visit and Visit 2.

In accordance with ICH E9 guideline on Statistical Consideration in the Design of Clinical Trials (1998), the type 1 error rate of the test will be 5%.

At each post-baseline visit, an analysis of covariance (ANCOVA) will be performed to test the null hypothesis of no treatment effect. The dependent variable will be the difference between the value at each post-baseline visit, including endpoint, and the baseline value. The change from baseline to the endpoint (Visit 6) will be the primary efficacy analysis. The baseline value will be the covariate. Treatment group and study center will be the main effects in the model. This analysis will be performed on the MITT and PP populations. Efficacy will be declared if the treatment effect p-value for the MITT population is no greater than 0.05 and is favorable to ACU-D1 Ointment [REDACTED].

A second ANCOVA, which includes a treatment-by-center interaction, will be performed in order to test the significance of the interaction term in an exploratory manner. If the interaction term is significant at the 0.10 level, summary data will be presented for each study center in an appendix to the study report. In addition, if the interaction term is significant at the 0.10 level, the interaction term may be included in the final ANCOVA model to examine treatment effects if inclusion of this term increases the sensitivity of the analysis.

The residuals from the primary ANCOVA model will be analyzed for deviations from normality. If the test for normality fails at the 0.05 level of significance then the ANCOVA analysis will be supplemented by a Van Elteren test, stratified by study center.

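### SAP 8.11.1 names change to Visit 6 as the primary endpoint but, as written, declares efficacy on a treatment effect averaged over Visits 3–7, contrary to protocol 9.3.2

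*SAP*

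**What the plan says.** SAP 8.11.1 sets out the primary analysis in one paragraph.

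- Model: "Proc Mixed in SAS will be used to develop a repeated measures analysis of covariance (ANCOVA) model". The response is the change from baseline at each post-baseline visit, with endpoint included.
- Terms: baseline as covariate, and "Treatment group and study center will be the main effects in the model".
- Endpoint: "The change from baseline to the endpoint (Visit 6) will be the primary efficacy endpoint".
- Decision rule: "Efficacy will be declared if the treatment effect p-value for the MITT population is no greater than 0.05", provided the direction favors the active ointment.

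Two interactions are named in the same section: "A second ANCOVA, which includes a treatment-by-center interaction, will be performed", and for subgroups, "Subgroups will be analyzed by adding the subgroup as a main effect and the interaction term" with treatment. Neither document gives a visit term, a treatment-by-visit term, a Visit 6 contrast or a covariance structure for this model.

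Baseline is Visit 2 (SAP 8.5.1) and lesions are counted at Visits 1–7 (protocol 6.1.1), so the post-baseline visits are 3, 4, 5, 6 and 7. SAP section 6 describes the last as "Visit 7 (Day 99) no treatment follow-up, end of study".

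Protocol 9.3.2 differs. It runs a separate ANCOVA at each post-baseline visit and states "The change from baseline to the endpoint (Visit 6) will be the primary efficacy analysis". It lists a mixed-model repeated-measures analysis over all post-baseline visits as exploratory and optional.

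**The concern.** In a repeated-measures model with only baseline, treatment and center, the treatment coefficient is a weighted average of the visit-specific effects. It equals the Visit 6 effect only when the effect is the same at every visit or happens to average to that value. The success rule therefore need not answer the question the named endpoint asks, and it can err in either direction. An effect that builds up to Week 12 can be missed, and an early effect that has gone by Week 12 can be declared efficacy. How much each visit counts depends on a covariance structure the SAP leaves open. A reader holding both documents also finds two different deciding tests.

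The likely origin is visible in the text. The protocol's term list and decision rule are adequate for one ANCOVA per visit. The SAP replaced the per-visit models with a single repeated-measures model and kept the rest.

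**Working it through.** **Is there a plan figure to reproduce?** No. Protocol 9.7 states that no data exist for a power calculation. The finding rests on the text, and the figures below only show its possible size.

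**Inputs from the documents.** 24 vs 12 subjects; two centers (SAP 4 and 6); 5% type I error, taken as two-sided with a favorable direction; five post-baseline visits.

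**Assumptions.** SD of adjusted change 1 at each visit; Visit 6 effect 1 SD where there is one; complete data; one record per visit; within-subject correlation ρ of 0.5–0.8. Three effect profiles, Visits 3 to 7, in SD units:

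- gradual: 0.25, 0.50, 0.80, 1.00, 0.70 (mean 3.25/5 = 0.65)
- constant: 1 throughout (mean 1.00)
- early only: 1, 1, 0.5, 0, 0 (mean 2.5/5 = 0.50)

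**Visit 6 test.** Standard error √(1/24 + 1/12) = 0.354. Noncentrality 1/0.354 = 2.83. Degrees of freedom 36 − 4 = 32 (intercept, baseline, treatment, one for two centers). Noncentral-t power: 78%. With no Visit 6 effect, the favorable rejection rate is 2.5%.

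**Averaged test, compound symmetry.** Each visit has weight 1/5 = 20%. The variance of a subject's mean is (1 + 4ρ)/5; at ρ = 0.6 this is 3.4/5 = 0.68, SD 0.825. Noncentrality = mean effect / (0.825 × 0.354):

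| Profile | Noncentrality (ρ = 0.6) | Averaged test (ρ = 0.6) | Other ρ | Visit 6 test |
|---|---|---|---|---|
| Gradual | 0.65/0.292 = 2.23 | 58% | 63% to 49% (ρ 0.5 to 0.8) | 78% |
| Constant | 1.00/0.292 = 3.43 | 91% | 94% to 85% (ρ 0.5 to 0.8) | 78% |
| Early only | 0.50/0.292 = 1.71 | 38% | 43% and 35% (ρ 0.5 and 0.7) | 2.5% |

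**Weights under AR(1).** The generalized least-squares weights are R⁻¹1 / (1′R⁻¹1), where R is the correlation matrix of the five visits. At ρ = 0.6 they are 0.31, 0.125, 0.125, 0.125, 0.31 for Visits 3–7. Over ρ = 0.5 to 0.8, Visit 6 receives 14% down to 8%, while off-treatment Visit 7 receives 29% up to 38%. The unstated covariance therefore changes what is being tested.

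**Simulation checks at ρ = 0.6.** A random-intercept model with baseline, treatment and center only (200 trials per profile, improvement negative) gave mean treatment effects of −0.66, −1.00 and −0.50 for the gradual, constant and early-only profiles. The true Visit 6 differences were −1.0, −1.0 and 0. Tests on subject means (20,000 trials) rejected in 57%, 91% and 37%. With no effect at any visit, the favorable rejection rate was 2.4%, so the type I error under the global null is not inflated.

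**Leaving out Visit 7 without a Visit 6 contrast.** Over Visits 3–6 at ρ = 0.6 the variance is (1 + 3 × 0.6)/4 = 0.70. Mean effects are 2.55/4 = 0.6375 (gradual) and 2.5/4 = 0.625 (early only). Gradual-onset power goes from 58% to 55%, and the early-only declaration rate from 38% to 54%. Removing Visit 7 alone does not cure the problem.

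**The case against.** The SAP never says that the effect is pooled; this follows only if the listed terms are complete. Other text points toward by-visit testing. The paragraph names Visit 6 before stating the rule, and it bases the comparison on each visit's difference from Visit 2. SAP 8.11.4 applies the primary method to individual lesion types at each visit. The stratified Van Elteren supplement normally takes one value per subject. The authors may well have meant a Visit 6 contrast. That is fair on intent, but the listed terms cannot produce a Visit 6 test, and the deciding contrast should not be left to the programmer.

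Second, including endpoint in the response could add a sixth record. If Visit 6 counts twice with equal record weights, its weight is 2/6 = 33%. At ρ = 0.6, gradual-onset power becomes 65% and the early-only declaration rate 28%. The sizes move but the direction does not.

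Third, the effect profiles are illustrative. Nothing in the documents suggests an early effect that vanishes, and with a constant effect the averaged test is the more powerful one. This stands as a limit on the figures.

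Fourth, restoring the Visit 6 ANCOVA is not quite enough. SAP 8.1 and protocol 9.2.1 define endpoint as the last non-missing post-baseline value, which for a completer could be Visit 7. This stands, and the fix should settle it.

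Finally, this is a 36-subject proof-of-concept study. It nevertheless sets a 5% error rate and a formal efficacy rule, and that rule should match its endpoint.

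**Conclusion.** The concern holds, limited to the SAP as written. The deciding p-value is not tied to Visit 6. With the listed terms it tests an effect averaged over Visits 3–7, one of them off treatment, and it gives the deciding role to a model the protocol calls exploratory. Confidence is high because this rests on the text.

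The size depends on assumed profiles, a common SD, complete data and five records per subject. At correlation 0.6, against 78% for a Visit 6 test, power could fall by 20 points (gradual onset) or rise by 13 (constant effect). Efficacy could be declared in 38% rather than 2.5% of trials in which the Visit 6 effect is zero after an early benefit. The fault is the wrong target. It lies in the one rule that decides success, so it must be fixed before unblinding.

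**What to change.** Amend SAP 8.11.1 in one of two ways.

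1. Preferred: restore the protocol's Visit 6 ANCOVA (baseline, treatment, center) as the deciding test and keep the repeated-measures model as supportive.
2. Otherwise: add categorical visit and treatment-by-visit terms, prespecify the covariance structure, limit the model to on-treatment Visits 3–6 with one record per visit, and declare efficacy on the Visit 6 treatment contrast, reported with its 95% confidence interval. Record the departure from protocol 9.3.2, with reasons, as an amendment before unblinding, as protocol 9.1 and SAP section 8 require.

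Either way, analyze Visit 7 separately and bring protocol 9.3.2 and SAP 8.11.1 into agreement. In the same edit, state that endpoint means Visit 6, so that the last-observation rule cannot bring in Visit 7, and say how missing Visit 6 values are handled under the chosen model.

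The cost is SAP wording and a few lines of SAS before unblinding. No new data and no additional subjects are needed.

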## **4. STUDY POPULATION**

Approximately 36 subjects, male and female, 18 years of age or older who meet all the inclusion criteria and none of the exclusion criteria will be enrolled at two United States investigational centers. Subjects will be randomized in a 2:1 ratio with 24 subjects randomized to treatment with ACU-D1 Ointment [REDACTED] and 12 subjects randomized to treatment with ACU-D1 Ointment Vehicle.

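### SAP 8.11.1 promises a 5% type 1 error but decides efficacy on a repeated-measures treatment effect that is pooled over visits as listed, does not test Visit 6, and can reject well above 5%

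*SAP*

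**What the plan says.** Protocol 9.3.2 sets a 5% type 1 error for this test: "At each post-baseline visit, an analysis of covariance (ANCOVA) will be performed to test the null hypothesis of no treatment effect". The change to Visit 6 is primary, baseline is the covariate, and treatment and center are main effects. Each fit uses one row per subject. Later in the same section, a mixed-model repeated-measures analysis across visits is offered as an optional exploratory analysis.

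SAP 8.11.1 keeps the error statement ("the type 1 error rate of the test will be 5" percent) and the decision rule ("Efficacy will be declared if the treatment effect p-value for the MITT population is no greater than 0.05", with the effect in favor of ACU-D1) but changes the test: "Proc Mixed in SAS will be used to develop a repeated measures analysis of covariance (ANCOVA) model to test the null hypothesis of no treatment". On the outcome it says: "The dependent variable will be the difference between the value at each post-baseline visit, including endpoint, and the baseline value". On the effects: "Treatment group and study center will be the main effects in the model", with baseline as covariate. On the time point: "The change from baseline to the endpoint (Visit 6) will be the primary efficacy endpoint". Missing values are filled by LOCF.

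Neither SAP 8.11.1 nor the general and missing-data text of SAP 8 and 8.1 names a visit term, a treatment-by-visit term, a within-subject covariance structure or a degrees-of-freedom method.

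**The concern.** The 5% statement fits the Protocol's test: with one row per subject and normal errors, the ANCOVA t-test is exact. It does not carry over automatically to several correlated rows per subject. There the false-positive rate depends on which treatment effect is tested, on the covariance structure, and on how the standard error and degrees of freedom are obtained.

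Two things go wrong if the listed effects are taken at face value. First, a model with treatment but no treatment-by-visit term yields one treatment effect averaged over all visits entered. That is not the Visit 6 change named as primary. It includes Day 15 and, if every post-baseline visit is used, the off-treatment Visit 7. Second, its p-value can exceed the stated error rate. This p-value is the only stated criterion for declaring efficacy, so a positive proof-of-concept result could be trusted more than it deserves. The choices left open could also be made after results are seen.

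**Working it through.** **Inputs from the documents.** 36 subjects: "Subjects will be randomized in a 2:1 ratio with 24 subjects randomized to treatment" with ACU-D1 and 12 to vehicle (SAP 4). Two centers (SAP 4 and 6). Post-baseline visits 3 to 6, or 3 to 7 if Visit 7 is included: m = 4 or 5 rows per subject. Two-sided threshold 0.05 plus favorable direction (SAP 8.11.1). LOCF makes the analyzed data complete.

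**Assumptions, not in the documents.** Normal errors and a between-visit correlation rho of 0.3 to 0.8. Protocol 9.7 says there are no earlier data, so no variance or correlation is given.

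**Step 1, the stated 5%.** In simulated null trials (8,000 per main scenario), the Protocol's Visit 6 ANCOVA rejected 4.5-5.3%. It reproduces the stated figure.

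**Step 2, pooled effect with visits treated as independent.** Independence is the Proc Mixed default structure. It understates the variance of the pooled effect by the factor 1 + (m - 1) x rho. The approximate two-sided rejection rate is 2 x [1 - Phi(1.96 / sqrt(1 + (m - 1) x rho))].

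| m | rho | factor | 1.96 / sqrt(factor) | approximate rate | simulated rate |
|---|---|---|---|---|---|
| 4 | 0.3 | 1.9 | 1.42 | 15.5% | 13-14% |
| 4 | 0.5 | 2.5 | 1.24 | 21.5% | 19-20% |
| 4 | 0.8 | 3.4 | 1.06 | 28.8% | 27-29% |
| 5 | 0.5 | 3.0 | 1.13 | 25.8% | 24-25% |
| 5 | 0.7 | 3.8 | 1.01 | 31.5% | 30-31% |
| 5 | 0.8 | 4.2 | 0.96 | 33.9% | 32-33% |

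The two ends of each simulated range are without and with a visit term. Adding visit alone does not help. If the endpoint is entered as an extra row repeating Visit 6, the rate at rho 0.7-0.8 is 30-39%.

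**Step 3, pooled effect with other structures.** An unstructured matrix has m(m + 1)/2 parameters: 10 for four visits, 15 for five.

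- Unstructured, default df (36 - 4 = 32): 7.0-7.6% with four visits and 8.1-9.2% with five. A five-visit serial-correlation scenario with 2,000 runs gave 9.6%, with a standard error of sqrt(0.096 x 0.904 / 2,000), about 0.7 points.
- Compound symmetry: 3.6-6.8%.
- Unstructured with Kenward-Roger: 4.4-6.2%, mean about 5.1% (500 fits per scenario, standard error about 1 point).

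**Step 4, rate in favor of ACU-D1.** Under the null, half of the rejections go each way. Unstructured with default df: 7.0/2 = 3.5% to 9.2/2 = 4.6%. Independence: 13/2 = 6.5% to 33/2 = 16.5%. A valid two-sided 5% test gives 2.5%.

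**Step 5, Visit 6 contrast from a treatment-by-visit model.**

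- Unstructured, default df: 4.6-5.6%.
- Independence: 5.3-6.6% if variances are equal across visits, 13-15% if the variance grows by Visit 6.
- Compound symmetry with variance growing by Visit 6: 15.6-16.8%, because one common variance is then too small for Visit 6.

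The unstructured inflation in Step 3 therefore belongs to the pooled effect, which combines visits with estimated weights. It does not appear at Visit 6.

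**The case against.** The strongest reply is that the SAP names Visit 6 as the primary endpoint, so a competent analyst would add treatment-by-visit and test the Visit 6 contrast. With an unstructured matrix that contrast holds about 5% even with default degrees of freedom. The numbers support this. What remains is that the SAP does not write that model: no listed term yields a Visit 6 p-value, and the efficacy rule refers to a single treatment effect.

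A second reply is that treating a subject's visits as independent contradicts the term repeated measures. That is fair. A reader might infer that the trial's false-positive rate will be 30% or more, and the documents do not support that. The figure needs the pooled test, the default structure, and an assumed correlation at the upper end or a duplicated endpoint row. Nothing in the SAP says independence is intended; the text merely fails to exclude it.

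A reader might also infer that any analysis with default degrees of freedom is inflated, or that a small-sample correction alone would cure the problem. Neither follows. The unstructured Visit 6 contrast needs no correction to hold about 5%, and Kenward-Roger on the pooled effect would give a calibrated test of the wrong quantity.

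Finally, efficacy requires a favorable direction, so the unstructured case means roughly 3-5% against 2.5%. That is a modest excess for a 36-subject pilot without a power calculation. It is still not the error rate stated.

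**Conclusion.** The primary model in SAP 8.11.1 is under-specified in a way that breaks its own 5% claim when run with the listed effects and common settings, and its treatment p-value then does not address the named Visit 6 endpoint. For that pooled effect the two-sided false-positive rate is about 7-9% with an unstructured matrix and default degrees of freedom (about 3-5% in favor of ACU-D1). It is about 13-33% with the default independent structure and about 5% with compound symmetry. The Visit 6 ANCOVA and an unstructured Visit 6 contrast both hold about 5%.

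These figures rest on 24 against 12 subjects, four or five visits, normal errors, complete data after LOCF, and an assumed correlation of 0.3 to 0.8. They do not cover other effects of LOCF or of non-normal counts. The SAP also promotes to primary a model that the Protocol treats as exploratory. The point should be corrected, at a weight suited to a proof-of-concept trial.

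**What to change.** Choose one of two remedies and reconcile SAP 8.11.1 with Protocol 9.3.2.

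1. Restore the Protocol's Visit 6 ANCOVA as the primary test and keep the repeated-measures model as exploratory. With LOCF-completed data, an unstructured Visit 6 contrast is essentially this ANCOVA, so little is lost.
2. Keep the repeated-measures model and state in SAP 8.11.1:
   - effects: baseline, center, treatment, visit and treatment-by-visit;
   - REPEATED visit / SUBJECT=subject TYPE=UN, with DDFM=KR;
   - TYPE=CS with DDFM=KR as the fallback for non-convergence. By Step 5 this protects the Visit 6 contrast only if variances are similar across visits; naming the Visit 6 ANCOVA as the fallback avoids that condition;
   - no separate endpoint row beside Visit 6, since under LOCF it would duplicate Visit 6 and make an unstructured matrix singular;
   - the efficacy p-value is that of the Visit 6 treatment contrast.

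The cost is a few sentences and SAS options. SAP 2 expects the SAP to be final before database lock, and SAP 8 allows amendments before unblinding. The downside is that the p-value may be slightly less favorable than under default settings.
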